- ‡ Subjects who roll-over from the UX001-CL203 study will not have a Month 2 or Month 4 visit. Assessments at these visits will only be performed for subjects who roll-over from the UX001-CL202 and UX001-CL301 studies. UX001-CL202 subjects will complete the same efficacy assessments as the subjects who rollover from UX001-CL301.
- a. Potential subjects can be screened up to 5 days after the last dose on the parent study. Baseline Visit should be not be more than 5 days after Screening visit. Subjects can have a concurrent Screening and Baseline visits. Study drug will be dispensed only after all study procedures at the Baseline Visit have been performed. For subjects who discontinue prior to completing the study, every reasonable effort should be made to perform the Early Termination (ET) procedures within four weeks of discontinuation.
- b. Interval history will include any signs, symptoms, or events (i.e. falls) experienced by the subject since the prior study visit that are not related to study procedure(s) performed at prior study visits or study drug. Interval history may include exacerbation or improvement in existing medical conditions (including the clinical manifestations of GNEM) that might interfere with study participation, safety, and/or positively or negatively impact performance of functional assessments.
- c. The physical examinations at Baseline/Screening, including a neurological examination; all others will be brief physical examinations. If a patient is unable to stand or has significant postural issues that interfere with collection of a standing height, self-reported adult height should be captured.
- d. Baseline C-SSRS administered at Baseline/Screening visit (may be same as last visit in parent study). Since Last Visit C-SSRS administered at all subsequent visits.
- e. Serum will be obtained at all study visits to evaluate creatine kinase (CK), serum SA and potential biomarkers of sialylation, and other markers of muscle injury and remodeling.
- f. Blood samples, preferably pre dose, and first-morning void urine will be collected to assess trough SA levels; record volume of urine collected.
- g. An aliquot from first morning void urine will be used for assessment of ManNAc; record volume of urine collected.
- h. Subjects should be instructed to return unused study drug and packaging to every visit. Note that all subjects being treated with 12 g/day Ace-ER in UX001-CL202 will be transitioned to 6 g/day Ace-ER dose in this protocol.

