#### **7.5.5.9    Adverse Events**

All AEs will be recorded from the time subjects sign informed consent for this extension study and completion of the End of treatment visit in the parent study until 30 days after the last dose of study drug. Adverse events reported as ongoing at parent study's End of

treatment visit and any new AEs prior to Baseline for this study will be reviewed and recorded at the Baseline visit.

The determination, evaluation, reporting, and follow-up of AEs will be performed as outlined in Section 8.5. At each visit subjects will be asked about any new or ongoing AEs since the previous visit. Assessments of AEs will occur at each study visit.

Clinically significant changes from study baseline in interval history, physical and neurological examination findings, vital signs, weight, clinical laboratory parameters, and concomitant medications will be recorded as AEs or SAEs, if appropriate.

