### **8.5.4 Adverse Event Reporting**

#### **8.5.4.1 General**

All AEs (i.e. any new or worsening in severity or frequency of a preexisting condition) with onset after the subject signs consent for study participation must be promptly documented on the CRF. The Principal Investigator is responsible for evaluating all AEs, obtaining supporting documents, and ensuring documentation of the event is adequate. Details of the AE must include severity, relationship to study drug, duration, and outcome.

All AEs will be recorded from the time subjects sign informed consent for this extension study and completion of the End of treatment visit in the parent study until 30 days after the

last dose of study drug. Adverse events reported as ongoing at parent study's End of treatment visit and any new AEs prior to Screening /Baseline visit for this study will be reviewed and recorded at the Screening/Baseline visit.

In addition, the Investigator should report any AE that occurs after this time period that is believed to have a reasonable possibility of being associated with study drug.

AEs ongoing at 30 days following the last dose of study drug should have a comment in the source document by the Investigator that the event has recovered, recovered with sequelae, or stabilized.

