8.7.1 Adverse Events

All AEs recorded from the time the subject signs the informed consent through the safety follow-up will be coded using the Medical Dictionary for Regulatory Activities (MedDRA version 17.1 or beyond).

The following AEs were collected:

- All AEs;
- All SAEs;
- Treatment-related AEs;
- Treatment-related SAEs;
- AEs leading to the discontinuation of study drug or discontinuation of study;
- Deaths.

The number and proportion of subjects with any treatment-emergent adverse events (TEAEs) (defined generally as any AE started on or after the first dose of study drug) will be summarized by System Organ Class (SOC), Preferred Term (PT), severity, grade, outcome and relationship to treatment for the following types of AEs. Additional summaries of subject incidence (by preferred term) will also be provided.

An AE continued from the parent study would be excluded since they were summarized in the parent study. However, if an AE continued from the parent study and the severity changed to worse will be considered as a TEAE and be summarized.

The severity of AEs will be based on Common Terminology Criteria for Adverse Events (CTCAE), Version 4.03. If an AE cannot be graded based on CTCAE, the investigator will assign a severity based on 1 = mild, 2 = moderate, 3 = severe, 4 = life threatening, and 5 = Death.

For those AEs that occurred more than once during the study, the maximum severity or highest grade will be used to summarize the subject incidence.

Detailed listings for all AEs, serious AEs, AEs leading to the discontinuation of study, and death will also be provided.

Subgroup analyses by gender, age (above and below median), and ethnicity (small group may be combined) will be performed to support the safety in GNEM patients.

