Number of subjects with treatment-related TEAEs	xx (xx.x)	xx (xx.x)	xx (xx.x)	xx (xx.x)	xx (xx.x)	xx (xx.x)	xx (xx.x)	
Number of serious TEAEs	xx (xx.x)	xx (xx.x)	xx (xx.x)	xx (xx.x)	xx (xx.x)	xx (xx.x)	xx (xx.x)	
Number of subjects with serious TEAEs	xx (xx.x)	xx (xx.x)	xx (xx.x)	xx (xx.x)	xx (xx.x)	xx (xx.x)	xx (xx.x)	
Number of TEAEs causing discontinuation	xx	xx	xx	xx	xx	xx	xx	
Number of subjects with TEAEs causing discontinuation	xx (xx.x)	xx (xx.x)	xx (xx.x)	xx (xx.x)	xx (xx.x)	xx (xx.x)	xx (xx.x)

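### A carried-over AE that turns serious or leads to stopping drug in CL302 at an unchanged grade is missing from the SAP's TEAE counts

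*SAP*

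**What the plan says.** SAP 8.7.1 builds its AE incidence summaries on TEAEs, "defined generally as any AE started on or after the first dose of study drug". For events already present at roll-over it says: "An AE continued from the parent study would be excluded since they were summarized in the parent study". One exception follows: "if an AE continued from the parent study and the severity changed to worse will be considered as a TEAE and be summarized". It gives no exception for an event that becomes serious or leads to discontinuation.

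The overall AE summary in SAP 10.7 uses the same base. Its serious rows count serious TEAEs, and its withdrawal row reads "Number of subjects with TEAEs causing discontinuation".

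SAP 4.1.1 defines the primary endpoint as the incidence and frequency of AEs and SAEs judged related to Ace-ER over the whole study. That wording has no carry-over exclusion. SAP 1 gives the SAP precedence over the protocol on analysis methods.

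Protocol 8.5.4.1 describes the AEs to be documented as "any new or worsening in severity or frequency of a preexisting condition". Protocol 8.5.2 states that serious and severe mean different things.

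**The concern.** CL302 enrols only subjects who completed a parent study, so some AEs will probably be ongoing at entry. What happens to such an event under CL302 treatment is part of what a long-term safety study is meant to show.

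The exclusion rests on the event having been reported already. That holds for the event as it stood at the end of the parent study. It does not hold for a later hospitalisation, or for a later decision to stop drug because of the event.

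The weakness is plainest for former CL301 placebo subjects. Their event was summarised under placebo. If it turns serious after they start Ace-ER, with no change of grade, no TEAE row in CL302 counts it.

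At stake are the serious-event and discontinuation counts and, for events judged related, the related-SAE count that serves the primary endpoint. The error can only go downward.

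**Working it through.** There is no planned figure to reproduce, because this is a counting rule and safety is summarised descriptively (SAP 8.7). The check applies the rule to an AE that is ongoing at roll-over and changes on or after the first CL302 dose.

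| Change in CL302 | Grade | TEAE under SAP 8.7.1? | Where it still appears |
|---|---|---|---|
| Severity worsens | higher | Yes | TEAE tables and listings |
| Becomes serious | unchanged | No | Listings only |
| Leads to stopping drug, subject stays in study | unchanged | No | Listings; SAP 8.2 does not clearly cover it |
| Leads to leaving the study | unchanged | No | Listings; disposition table with reasons (SAP 8.2) |
| Becomes more frequent | unchanged | Only if entered as an AE with onset after first CL302 dose | Depends on how the site records it |

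Rows two to four are the gap. Row two can occur because an event may meet a seriousness criterion without a grade change (protocol 8.5.2). Protocol 8.5.4.1 names severity and frequency as the changes that make a pre-existing condition an AE. It therefore gives the site no clear prompt to open a new record when only seriousness changes.

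**Scale.** The documents do not say how many AEs are ongoing at roll-over, so a corrected total cannot be computed. What one omitted subject is worth can be shown at the protocol's planned numbers (7.6.1): 55 + 80 + 30 = 165.

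- One subject is 1/165 = 0.6% overall, 1/80 = 1.25% of CL301, 1/55 = 1.8% of CL202 and 1/30 = 3.3% of CL203.
- Exact (Clopper-Pearson) 95% limits. With no events the upper limit is 1 − 0.025^(1/n), which gives 2.2% for n = 165 and 11.6% for n = 30.
- With one related SAE restored, 0/165 becomes 1/165 (0.6%, 0.02% to 3.3%), and 0/30 becomes 1/30 (3.3%, 0.1% to 17.2%).
- At the SAP's figure of about 180 subjects, one subject is 1/180 = 0.56%, so the choice between 165 and 180 does not matter here.

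**Illustrative range, assumed and not from the documents.** Suppose 10% to 50% of subjects carry over an AE, and 2% to 10% of those have one that turns serious or causes withdrawal at an unchanged grade. The number omitted then runs from 165 × 0.10 × 0.02 = 0.3 to 165 × 0.50 × 0.10 = 8 subjects.

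For context, protocol 5.2.4 reports no treatment-related SAEs and one AE withdrawal over about 2.5 years. Against counts that small, a single omission could change a statement that none occurred.

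**The case against.** The other side has good points.

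- **Nothing is lost from the data.** SAP 8.7.1 lists all AEs and SAEs, protocol 7.6.6 adds a by-subject listing of SAEs and of AEs linked to withdrawal from study or drug, and SAP 8.2 tabulates study discontinuations with reasons. This stands. It confines the defect to the AE summary tables.
- **Avoiding double reporting across parent and extension reports is a fair aim.** It is, but a footnote meets it without dropping a change that happened in CL302.
- **A serious event or a withdrawal will often bring a higher grade and so be counted.** Probably so, and this limits the number affected. It does not cover those whose grade stays the same.
- **The SAP 10.7 tables are examples.** True, but the exclusion itself is in the text of 8.7.1.

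Some stronger readings are tempting, and the documents do not support them.

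- A reader might infer that every frequency worsening drops out. Protocol 8.5.4.1 already has such a worsening documented as an AE, and one entered with onset after the first CL302 dose is a TEAE. The SAP only needs to say so.
- A reader might infer that the whole primary endpoint is compromised. It covers related events only, and discontinuation is not part of it.
- A reader might point to the gastrointestinal events in protocol 5.2.4 that were more common on treatment. The same paragraph says that exposure-adjusted rates at 6 g/day were similar to placebo.
- A reader might compare one or two hypothetical omissions with the single earlier withdrawal and speak of a doubling or tripling. That is not an estimate for CL302.
- A reader might add AEs that start between the last parent dose and the first CL302 dose, since "treatment visit and any new AEs prior to Baseline for this study will be reviewed and recorded at the Baseline visit". The visit rules allow at most 5 + 5 = 10 days from last parent dose to Baseline, and Screening and Baseline may coincide. These events precede CL302 dosing, and the documents do not show whether the parent reports count them. That is a separate and weaker question.

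**Conclusion.** The point holds in a narrow form. Under SAP 8.7.1, a continuing AE that becomes serious or leads to discontinuation on or after the first CL302 dose, at an unchanged grade, is left out of the serious-TEAE and discontinuation counts. If it is judged related and serious, it is also left out of the related-SAE count that serves the primary endpoint. The stated reason for the exclusion does not reach a change that occurs in CL302.

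The result is a downward bias in the AE summary tables, with no loss of data. Its size is unknown and probably small: each omitted subject is 0.6% of 165, or 3.3% of the 30 from CL203. This conclusion rests on two assumptions: that the severity exception is the only one, as the text reads, and that sites do not open a new AE record when only seriousness or treatment status changes.

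**What to change.** In SAP 8.7.1:

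1. Keep the severity exception, and also count a continuing AE as a CL302 TEAE if, on or after the first CL302 dose, it becomes serious or leads to discontinuation of drug or study.
2. Tabulate all SAEs and all AE discontinuations that occur on or after the first CL302 dose, whatever the AE onset date. Footnote those also reported in the parent study.
3. State that a worsening in frequency recorded as an AE after the first CL302 dose is a TEAE, in line with protocol 8.5.4.1.

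A rule based on newly judged relatedness, or on frequency derived from the data, is not proposed. The AE details required in protocol 8.5.4.1 include neither frequency nor the date on which a relatedness judgement changed.

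The cost is SAP wording and programming, using seriousness and discontinuation data that the study already collects. Counts may become slightly less favourable, and some events will appear in both the parent and the extension reports.

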8.7.1.1 Adverse Events to Monitor

Adverse events to be monitored are included in Appendix [10.5](#) by MedDRA preferred terms in categories of gastrointestinal AEs and liver-related investigations.

Tables summarizing patient incidents for the monitored adverse events will be generated.

8.7.2 Concomitant Medication

The number and percent of concomitant medications in CL302 will be summarized by ATC class and preferred term (per WHO-drug dictionary) in the safety analysis set.

If a subject took a specific medication multiple times or took multiple medications within a specific therapeutic class, that subject will be counted only once for the coded drug name or therapeutic class.

8.7.3 Clinical Laboratory Parameters

Descriptive statistics for clinical laboratory values and changes from the CL302 baseline values at each visit will be presented. The number and percentage of abnormalities for each lab parameter at each assessment time point will be reported.

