#### **7.5.2.8 Creatine Kinase Levels**

CK is a biochemical marker of muscle injury in many muscular system disorders. Most GNEM patients have some modest elevation of CK; in approximately 50% of patients CK levels are increased at least two-fold above the upper limit of normal (ULN). CK levels in serum will be measured as indicated in the Schedule of Events ([Table 2.1](#)) to assess the degree of reduction associated with treatment.

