**Table 7.5.5.5.1: Clinical Laboratory Assessments for Safety**

Chemistry	Hematology	Urinalysis+
Alanine aminotransferase (ALT)	Hematocrit	Appearance
Alkaline phosphatase	Hemoglobin	Color
Amylase	Mean corpuscular hemoglobin (MCH)	pH
Aspartate aminotransferase (AST)	MCH concentration (MCHC)	Specific gravity
Bilirubin (direct and total)	Mean corpuscular volume (MCV)	Ketones
Blood urea nitrogen (BUN)	Platelet count	Protein
Calcium	Red blood cell (RBC) count	Glucose
Chloride	Reticulocyte count	Bilirubin
Cholesterol (total)	Neutrophil count (absolute and %)	Nitrite
Creatine kinase 		Urobilinogen
Creatinine	Lymphocyte count (absolute and %)	Hemoglobin
Gamma-glutamyl transpeptidase (GGT)	Monocyte count (absolute and %)	Creatinine 
Glucose	Eosinophil count (absolute and %)	ManNAc 
Lactate dehydrogenase (LDH)	Basophil count (absolute and %)	Leukocyte esterase
Lipase	White blood cell (WBC) count	Pregnancy test (if applicable)
Phosphorus	WBC differential	Blood/RBC
Potassium		
Protein (albumin and total)		*Special assessment
Sodium		Serum pregnancy test if a positive urine pregnancy test
Triglycerides		

+ Microscopic examination will be performed only if dip stick is abnormal for protein, leukocyte esterase, blood or nitrite. Microscopic examination may include WBC,

RBC, Epithelial Cells, Squamous, Epithelial Cells, Transitional, Epithelial Cells, Renal Tubular, Hyaline Casts, WBC Casts, RBC Casts, Waxy Casts, Granular Casts, Calcium Oxalate Crystals, Uric Acid Crystals, Triphosphate Crystals, Yeast, Bacteria, Amorphous Urates and Amorphous Phosphates

 Also designated as PD variable (Section 7.5.2.8)

 Relevant to Drug Concentration Measurements (Section 7.5.3)

 To screen for use of prohibited medications (Section 7.4.6.1)

Subjects who experience a SAE possibly or probably related to study drug or other AE of concern may, at the discretion of the Investigator (and/or medical monitor), have additional blood samples taken for safety laboratory tests.

Upon completion of protocol-specified laboratory tests, leftover blood and urine samples from each visit may be used for additional exploratory research, eg, biomarker research. The leftover samples from this study will not be used for genetic testing.

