#### **7.6.6 Safety Analyses**

Safety will be evaluated for the overall study population as well as for subjects from the UX001-CL202, UX001-CL301, and UX001-CL203 study.

The safety analysis set will be used for the analyses of all safety endpoints. Safety will be evaluated by the incidence, frequency and severity of AEs and SAEs, and clinically significant changes from study baseline to scheduled time points in:

- Interval history
- Vital signs
- Physical examination findings
- Clinical laboratory evaluations
- Suicidal ideation and behavior assessments (C-SSRS)
- Concomitant medications

All AEs will be coded using the Medical Dictionary for Regulatory Activities (MedDRA). The incidence and frequency of AEs will be summarized by System Organ Class (SOC), Preferred Term (PT), severity, and relationship to treatment. The numbers (frequency) and incidence rates of AEs and SAEs will be summarized by treatment group. A by-subject listing will be provided for those subjects who experience a SAE, including death, or experience an AE associated with early withdrawal from the study or study drug treatment.

Clinical laboratory data will be summarized by the type of laboratory test. The frequency and percentage of subjects who experience abnormal clinical laboratory results (i.e. outside of reference ranges) and/or clinically significant abnormalities will be presented for each clinical laboratory measurement. For each clinical laboratory measurement, descriptive statistics will be provided for study baseline and all subsequent post-treatment scheduled visits. Changes from study baseline to the post-treatment visits will also be provided.

Changes in findings from study baseline physical examinations will be tabulated for each subject by examination category. If there are examination findings that change in more than one subject, these will be tabulated in a separate table and expressed as the number of subjects with the change out of the total. No statistics will be applied to the physical examination findings.

The SAP will provide additional details on the planned safety analyses.

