4.1.2 Other Safety Endpoints

Other safety endpoints include clinically significant changes from baseline to scheduled time points in the following:

- Interval History
- Vital signs
- Physical examination results
- Clinical laboratory results
- C-SSRS (a measure of suicidal ideation and behavior)
- Concomitant medications

Drug concentration endpoints will be evaluated for the following:

- Changes from baseline in free SA level in serum;
- Changes from baseline in urine SA level;
- Frequency and percentage of subjects with the presence of ManNac detected from urine testing.

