7.2.5 Visit Time Windows

There is no visit time window applied to handle the missing values for a scheduled visit. Nominal visits will be used for by-visit analyses. If an unscheduled visit has to be used, the principle of proximity will be applied.

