8 STATISTICAL METHODS OF ANALYSES

8.1 General Principles

All statistical tests will be two-sided and a difference resulting in a p-value of less than or equal to 0.05 will be considered statistically significant. All p-values will be rounded to and displayed in four decimals. If a p-value less than 0.0001 occurs, it will be shown in the table as <0.0001.

Continuous variables will be summarized by number of subjects and mean, SD/SE, median, minimum, and maximum values. Categorical variables will be summarized by number and percentage. No imputation on missing data will be made, unless stated otherwise.

Data collected will be presented in listings. Data not subject to analysis according to this plan will not appear in any tables or graphs but will be included in the data listings.

Post-hoc exploratory analyses not identified in this SAP may be performed to further examine the study data. These analyses will be clearly identified as such in the final clinical study report. The SAP will not be amended for post-hoc or additional analyses identified after planned analyses are completed. Similarly, additional tables and figures may be defined to further evaluate study results and the SAP will not be amended to list them.

Efficacy analyses will be presented by the parent study as illustrated in [Table 8.1.1](#): UX001-CL301, CL202 or CL203. Different efficacy endpoints at different scheduled time points were collected depending on which parent study the subjects were enrolled from.

Safety analyses will be presented by the parent studies and overall as illustrated in [Table 8.1.1](#). Subjects enrolling from UX001-CL301 will be further examined by the treatment group assigned in the parent study: placebo, Ace-ER 6 g/day, and All.

[Table 8.1.1](#) also provides the guidance for the treatment groups to be displayed for biomarker analyses as well as efficacy analyses and safety analyses, which have been described above. Baseline used for the analyses are specified as well. Example table templates are provided in [Appendix 10.6](#) for efficacy and safety.

Table 8.1.1: Analysis Presentation

Analysis Category	Analysis Set	Parent Study	Treatment Group	Baseline Applied	
Week 96/ET efficacy analysis	Full Analysis Set	CL301	Placebo*	Parent Study Baseline	
			Ace-ER 6 g/day		
			Placebo*	Current Study Baseline	
			ACE-ER 6 g/day		
			All		
Week 96/ET efficacy analysis	Full Analysis Set	CL202	Ace-ER 6 g/day	Current Study Baseline	

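### The planned laboratory tables do not show how many subjects worsen from their own baseline, and the protocol's count of clinically significant abnormalities is not carried into the SAP

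*SAP*

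**What the plan says.** SAP 8.7.3 has two sentences on laboratory data. The first: "Descriptive statistics for clinical laboratory values and changes from the CL302 baseline values at each visit will be presented". SAP 8.1 fixes the content of those statistics: "Continuous variables will be summarized by number of subjects and mean, SD/SE, median, minimum, and maximum values". The second: "The number and percentage of abnormalities for each lab parameter at each assessment time point will be reported". Direction, grade, multiple of the upper limit of normal (ULN), baseline status and worst post-baseline value are not mentioned, and SAP 8.7.3 does not define an abnormality.

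SAP 4.1.2 states the endpoint: "Other safety endpoints include clinically significant changes from baseline to scheduled time points in the following", and clinical laboratory results are on that list. Protocol 7.6.6 plans the frequency and percentage of subjects with results outside the reference range "and/or clinically significant abnormalities will be presented for each clinical laboratory measurement". SAP section 1 gives the SAP precedence over the protocol on analysis methods.

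The laboratory notes below Protocol Table 7.5.5.5.1 say that a subject with a possibly or probably drug-related SAE, or another AE of concern, may "have additional blood samples taken for safety laboratory tests". SAP 7.2.5 says: "Nominal visits will be used for by-visit analyses". It then allows an unscheduled visit to be assigned by proximity where one is needed, without saying when that is.

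On starting levels, Protocol 7.5.2.8 says that "in approximately 50% of patients CK levels are increased at least two-fold above the upper limit of normal". Protocol 5.2.4 reports mild transaminase elevations and attributes them mainly to the muscle disease.

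**The concern.** Long-term safety is the primary objective, and there is one open-label arm. Without a concurrent control, the main laboratory signal is a subject's change from his or her own baseline. The natural question is how many subjects got worse, and by how much. No planned laboratory table answers it.

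The abnormality count is least informative where the disease itself pushes results out of range. A subject whose CK goes from 2 to 10 times ULN is abnormal at both visits and is counted the same way twice.

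The SAP also names clinically significant change as an endpoint but has no laboratory table that counts subjects with one, because the protocol's category is absent from SAP 8.7.3. Finally, a peak found only at a for-cause draw has no defined place in the summary tables.

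**Working it through.** The documents state no laboratory figure to reproduce. The check sets the passages side by side and then illustrates the size with assumed inputs.

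**1. What each planned output can show**

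| Output | Subject already abnormal who worsens | Number of subjects who worsened |
|---|---|---|
| Count of abnormalities per time point | No change | Not shown |
| Change from baseline: n, mean, SD/SE, median, min, max | Moves mean, SD and maximum | Not shown |
| Listings (SAP 8.1) | Visible line by line | Not summarised |
| AE tables (SAP 8.7.1) | Visible if recorded as an AE | Only those recorded as AEs |

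**2. The abnormality count**

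Inputs: N = 165 (Protocol 7.6.1) or 180 (SAP 3.5). Assumptions: share b abnormal at baseline; share w of those worsens threefold; nobody normalises and nobody becomes newly abnormal.

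- Percentage abnormal before = percentage abnormal after = bN / N.
- Subjects worsened = w × bN.
- N = 165, b = 50%: 0.50 × 165 = 82.5, taken as 82; 82/165 = 49.7% before and after.
- w = 5%: 0.05 × 82 = 4.1, about 4 subjects (2.4% of 165).
- w = 10%: 8.2, about 8 (4.8%).
- w = 20%: 16.4, about 16 (9.7%).

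Over b from 30% to 80% and w from 5% to 20%, the worsened number 2 to 26 at N = 165 (1.2% to 15.8%) and 3 to 29 at N = 180 (1.7% to 16.1%). The percentage abnormal does not move in any of these cases.

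**3. The change-from-baseline table**

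A simulation of 165 subjects drew about half with a baseline median of 3 × ULN and the rest with 0.6 × ULN, adding noise of 10% of the baseline value. The share abnormal was 50.3% at baseline and 49.7% afterwards for every w (a net one subject, from noise). Changes in multiples of ULN:

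| w | Mean | SD | Median | Maximum |
|---|---|---|---|---|
| 0% | 0.01 | 0.21 | 0.01 | 0.75 |
| 5% | 0.17 | 1.02 | 0.01 | 7.68 |
| 10% | 0.33 | 1.48 | 0.01 | 8.12 |
| 20% | 0.66 | 1.97 | 0.02 | 8.12 |

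This table does register that something happened. It does not say to how many: when the share worsening doubles from 10% to 20%, the maximum stays at 8.12. A mean cannot separate a few large rises from many small ones.

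**4. Per-visit against any-post-baseline**

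Suppose 10% of subjects each have one transient abnormality, spread evenly over visits. A per-visit table then averages 10%/6 = 1.67% on the CL202/CL301 schedule (six post-baseline visits) and 10%/4 = 2.5% on the CL203 schedule (four). A count of subjects with any post-baseline abnormality gives 10% in both.

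**The case against.** The strongest reply is that the laboratory plan is more than a percentage abnormal. Changes from baseline come first in SAP 8.7.3, with minimum and maximum, and a rise from 2 to 10 × ULN at a visit would put that visit's maximum change at 8 × ULN or more. CK also has its own change-from-baseline summaries as an efficacy or exploratory endpoint (SAP 10.1). Under Protocol 7.5.5.9, clinically significant laboratory changes are recorded as AEs where appropriate. Those are graded by CTCAE 4.03 and summarised at maximum severity (SAP 8.7.1), and liver-related terms are tabulated separately (SAP 8.7.1.1 and 10.6.2). All this stands. A reader might infer that the planned output as a whole would look flat while subjects worsen; the documents do not support that.

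A reader might also infer that unscheduled bloods are left out. They are not expressly excluded. SAP 8.7.3 speaks of assessment time points, whereas the vital-signs section (8.7.4) specifies scheduled visits, and SAP 7.2.5 allows assignment by proximity. Their handling is undefined. Early-termination samples are already covered, since Table 8.1.1 describes the safety analysis as Week 96/ET.

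What the reply does not supply is a count. A maximum describes one subject per visit, listings give no incidence, and AEs depend on what the investigator judges reportable. The monitored liver terms include no CK term.

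**Conclusion.** The point holds as a gap in what is counted. The abnormality table cannot register worsening in subjects already out of range, no planned laboratory table gives the number of subjects who worsened or by what category, and the SAP drops a subject-level count that the protocol promised and its own endpoint calls for. It is a cheap improvement to a descriptive safety analysis; it does not show that a signal would be missed.

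The size cannot be fixed from the documents. It is tempting to apply the 50% CK figure to the planned sample (82.5 of 165, or 90 of 180) and call that the number of subjects affected. That figure describes patients with the disease in general. Subjects from CL202, CL203 and the active arm of CL301 arrive already treated, Protocol 5.2.4 says treatment lowers CK, and Protocol 7.5.6 describes CK in these patients as mildly raised or normal. The CL302-baseline share is therefore unknown, and no transaminase rate is given. The 4, 8 and 16 subjects above are illustrations under assumed b and w. The blindness of the count itself needs only that some subjects start out of range.

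**What to change.** Keep both outputs in SAP 8.7.3 and add:

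1. Shift tables from CL302 baseline to worst post-baseline value, using all post-dose results, including unscheduled ones. Use CTCAE 4.03 grade where one exists, multiples of ULN for CK, ALT and AST, and low/normal/high otherwise.
2. The number and percentage of subjects worsening by at least one grade and by at least two grades.
3. The protocol's number and percentage of subjects with clinically significant abnormalities, per analyte, with a statement of who makes that judgement.
4. A definition of an abnormality, and a rule for when an unscheduled result enters a by-visit table.

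The SAP already uses CTCAE 4.03 and maximum severity for AEs, so items 1 and 2 extend its own convention. No new samples are needed for the shift tables; the cost is SAP wording and standard programming.

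There is one small analytic cost. Worst-value counts rise with the number of draws, which is four post-baseline visits for CL203 against six for CL202 and CL301, plus any samples triggered by AEs. The tables should be shown by parent study as well as overall, with a footnote saying so.
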